**Table-2: Screening and Visits**

	Screening	Day 0	Week 2	Week 4	Week 6	Week 8	Week 10	Week 12	Week 18
Ixekizumab		X	X	X	X	X	X	X	
Physical Exam	X	X	X	X	X	X	X	X	X
Adverse Event Assessment		X	X	X	X	X	X	X	X
Chest X-ray	X								
BPDAl		X	X	X	X	X	X	X	X
Photographer		X	X	X	X	X	X	X	X
ECG	X								
Venipuncture	X	X		X		X		X	
Serum Pregnancy Test	X								
anti-BMZ autoantibodies	X								
CRP-C reactive protein	X								
anti-BP230 IgG	X	X		X		X		X	
anti-BP180 IgG	X	X		X		X		X	
CMP	X					X			
CBC	X	X		X		X		X	
Quantiferon Gold	X								
Hepatitis B	X								
Hepatitis C	X								
HIV	X								
Coccidioidomycosis	X								
HbA1c	X								
Interleukin 6, 17, 22, 23		X		X		X		X	
TGFb- Transforming growth factor beta		X		X		X		X	
MMP-9 Matrix-metalloprotease-9		X		X		X		X	

## **Supplementals:**

### **Supplemental 1: Appropriateness of Measures**

According to expert consensus guidelines on BP, new blister formation is a defining feature of disease activity. (6) Disease control is defined as the cessation of new blister formation. The consolidation phase is defined as the phase with no new blister formation in 2 weeks and healing of lesions. Transient lesions heal within 1 week and non-transient lesions are does not heal within 1 week. Complete remission is defined by, no new blisters within 2 months, on or off therapy. Partial remission is defined by transient lesion formation. New, mild disease activity is defined by the formation of less than 3 lesions per month and a disease flare is defined by 3 or more lesions in a month. Therefore, we will be required to monitor for the time to cessation of new blisters as surrogate for disease control as well as the formation of new blisters throughout the study.

BPDAI will be used for calculation of the overall disease activity in BP. The BPDAI is a standard, objective and subjective scoring system for cutaneous disease activity and pruritus respectively in BP. The pemphigus disease activity index (PDAI) has been validated in a different auto-immune blistering disease which shares some characteristics with BP. (23) Currently, the BPDAI is undergoing validation studies and it represents the most current method of objectively scoring BP. (24) The two BPDAI indices capture disease activity and quality of life. Additionally, current studies have found that the degree of cutaneous involvement at initial diagnosis, which would be captured by the BPDAI, is predictive of the likelihood of a subsequent flare. (25) Therefore, the data collected by the BPDAI is useful in the analysis of flares in the follow up phase. The BPDAI consists of scoring various types of lesions and creates a score out of 120 (see below left). A score of greater than 56, on the objective portion, has been considered severe disease. (24) Note that we will be using 5% body surface area (BSA) of disease or moderate to extensive disease (Moderate to extensive Bullous Pemphigoid defined by the mean number of new bullae and urticarial plaques that have appeared over the course of 3 days as determined by the investigator or referring physician (moderate disease defined by  $> 1$  and  $\leq 10$  new bullae and  $\geq 5$  urticarial plaques and extensive disease by  $>10$  new bullae)) as our initial criteria for enrollment in the study. In our clinical experience, 5% BSA represents a simple, clinical cutoff for disease requiring systemic agents. Formal BPDAI will not be conducted prior to enrollment.

BPD AI					
SKIN	ACTIVITY		ACTIVITY		DAMAGE
Anatomical location	Erosions/Blisters	Number of Lesions if <3	Urticaria/ Erythema / Other	Number of Lesions if <3	Pigmentation / Other
	0 absent		0 absent		Absent 0, present 1
	1 1-3 lesions, none > 1 cm diameter		1 1-3 lesions, none > 6 cm diameter		
	2 1-3 lesions, at least one > 1 cm diameter		2 1-3 lesions, at least one lesion > 6 cm diameter		
	3 >3 lesions, none > 2 cm diameter		3 >3 lesions, or at least one lesion > 10 cm diameter		
	5 >3 lesions, and at least one > 2 cm		5 >3 lesions and at least one lesion > 25 cm		
	10 >3 lesions, and at least one lesion > 5 cm diameter or entire area		10 >3 lesions and at least one lesion > 50 cm diameter or entire area		
Head					
Neck					
Chest					
Left arm					
Right arm					
Hands					
Abdomen					
Genitals					
Back/Buttocks					
Left leg					
Right leg					
Feet					
Total skin	/120		/120		
MUCOSA	Erosions/Blisters				
	1 1 lesion				
	2 2-3 lesions				
	5 >3 lesions, or 2 lesions > 2cm				
	10 entire area				
Eyes					
Nose					
Buccal mucosa					
Hard palate					
Soft palate					
Upper gingiva					
Lower gingiva					
Tongue					
Floor of Mouth					
Labial Mucosa					
Posterior Pharynx					
Anogenital					
Total Mucosa	/120				

**BPD AI PRURITUS COMPONENT - VAS**

DATE: .....

- Baseline
- Consolidation phase
- Tapering phase
- Complete remission on minimal therapy
- Complete remission off therapy
- Beginning Consolidation
- End of Consolidation
- Partial remission on minimal therapy
- Partial remission off therapy
- Flare

**A. How severe has your itching been over the last 24 hours?**

0 1 2 3 4 5 6 7 8 9 10  
None Severe

Score out of 10 =

**B. How severe has your itching been the past week?**

0 1 2 3 4 5 6 7 8 9 10  
None Severe

Score out of 10 =

**C. How severe has your itching been in the past month?**

0 1 2 3 4 5 6 7 8 9 10  
None Severe

Score out of 10 =

Average INTENSITY SCORE FOR PAST MONTH = (A+B+C) = /30

OR

For BP patients with impaired mental functioning:

No evidence of itch (no excoriations)	0
Mild itch (isolated excoriations up to two body sites)	10
Moderate itch (excoriations on ≥ 3 body sites, impairment of daily activity)	20
Severe itch (generalized excoriation, sleep impairment)	30
TOTAL SCORE	/30

Adapted from: (6)

The subjective portion of the BPD AI is the pruritus component (see above right). This component is key to document as one of the major causes of morbidity in BP, in addition to the blistering, is the diffuse pruritus. Again, this test is undergoing validation currently and represents the most up to date measure for itch in BP.

Prednisone is the mainstay of therapy in BP and the dosage of prednisone correlates with disease activity. (11, 13, 18, 24) In this study, prednisone will be offered as a rescue therapy throughout the study (see [Supplemental 4](#)). This allows for examine the efficacy of Taltz (Ixekezumab) as a monotherapy, as well as its efficacy as a steroid-sparing agent. Oral corticosteroids will provide comfort, if needed, during the initiation phase of Taltz (Ixekezumab). All individuals on prednisone will be placed on Calcium 1200mg and Vitamin D 800IU.

ELISA Measurements for BPAG1 and 2 are the standard of care for diagnosis of BP. This test will be run centrally at the Mayo Medical Laboratory (MML) in Rochester Minnesota. The antibody levels, of BPAG2, correlate with disease activity. (26) Therefore, it is critical to monitor these antibody levels as this is a marker of disease severity and may be important in judging both a cutaneous and serological response to Taltz (Ixekezumab).

The exploratory variables examined in this study will aim to correlate the clinical responses in BP patients with both systemic and local changes in the cytokine milieu. The Th17 inflammatory response is a key pathway in autoimmune, inflammatory diseases. (27) The most efficacious therapies in psoriasis target the Th17 pathway with IL-17 and IL-23 blockade. (28-30) The key cytokines in the Th17 pathway are IL-6, -17, -22, -23, and TGFb. These cytokines play a complex role in the pro- and anti-inflammatory response. (27) IL-6 is a pro-inflammatory cytokine that, when present with IL-23, leads to Th17 polarization. Th17 cells release IL-17 which produces a biological cascade of inflammatory molecules including: tumor necrosis factor alpha (TNFα),

IL-1 $\beta$ , GM-CSF, IL-6, IL-8, and MMP-9. (31) MMP-9 is elevated in blister fluid and serum of patients with BP and IL-17 is elevated in the blister fluid. (5, 32) Treatment with topical corticosteroids has been shown to decrease lesional MMP-9 and IL-17 levels, which correlated better with clinical improvement than did the BPAG1 and 2. (33) Therefore, following these IL-6, -17, -22, -23, TGF $\beta$ , and MMP-9 during therapy in treatment naïve and refractory disease may provide insight into the early and late pathogenesis in BP. Additionally, our findings may support the use of other serological biomarkers for monitoring disease activity as well as predicting therapeutic success in BP with the targeting of IL-17.

TGF $\beta$  plays a particularly complex role in the pro- and anti-inflammatory response. TGF $\beta$ , when present in the absence of IL-6, -17, and -23, generates T-regulatory cells. The pathogenesis of T-regulatory cell generation and the resolution phase of inflammatory diseases have remained unclear; however, recent studies suggest that there may be a process of trans-differentiation of Th17 cells into T-regulatory cells. (34, 35) While the mechanism is still being deciphered, it appears that IL-17A receptor plays a key role in the formation of T-regulatory cells and it may be possible that IL-17A blockade is efficacious by not only down-regulating the Th17 response but by also up-regulating the T-regulatory response. A recent article in the journal, *Nature*, found that the Th17 cells themselves might be transdifferentiating into T-regulatory cells. (34) This has tremendous implications and may suggest the broad utility of IL-17A blockade in inflammatory diseases. However, more studies are needed to confirm these findings as well as the extent of plasticity of Th17 cells in inflammatory disease. If this current study is funded by Lilly, our group will be submitting for additional funding to examine the T-cell population during therapy to determine if the role that IL-17A blockade plays in T-regulatory cell formation and disease response.

In order to assess the inflammatory milieu of the blister and serum, a routine blood draw prior to drug therapy will be performed on the designated days and the serum will be stored for future use. The peripheral blood will be drawn and stored according to prior established protocols. Additionally, one active, tense blister will be drained using a needle and syringe. A minimum of 0.5cc of blister fluid and a maximum of 5cc of blister fluid will be stored via a simplified version of the serum protocol.

Our laboratory will perform a multiplex cytokine analysis on serum and blister fluid for Interleukin (IL)-6, -17, -22, -23 on an ELISA assay. Similar array based assays will be used for Transforming Growth Factor beta (TGF $\beta$ ) and matrix-metalloprotease-9 (MMP-9) expression. The serum and blister fluid will be stored per protocol and a single batch of samples at weeks 0, 4, 8, 12 will be run in parallel and in duplicate at the end of the study.

Finally, we will use RNA sequencing by Nanostring technology to examine the Gene expression changes in inflammatory pathways and correlate these changes with the cytokine analysis. We will examine the gene expression changes in the blister fluid, blood, and archival tissue samples. For archival tissue samples from each subject, we will use up to 100 microns of tissue to extract RNA.

## **Supplemental 2: Safety Measures**

### **Baseline Screening:**

A QuantiFERON® TB-Gold In-Tube assay will be performed to assess the TB status at screening for all subjects. This test will only be used to determine subject's eligibility for the trial. The test will be used to screen the subject population for latent tuberculosis infection. This blood-based assay is specific for *Mycobacterium tuberculosis* and is not influenced by previous *Bacillus Calmette-Guérin* vaccination or exposure to other *Mycobacteria* species. This test, in contrast to the purified protein derivative (PPD) skin test, is also insensitive to a booster effect since the subject is not exposed to the vaccine. The assay measures the production of interferon-gamma and presents it relative to a negative and a positive control sample. (36)

- If the test result is negative, the subject may be enrolled in the study
- If the test result is positive, the investigator should perform workup for the test result as per local procedures

- Subjects **positive** for latent TB per workup may enter the study if sufficient treatment has been initiated according to local routine clinical practice and will be maintained for the prescribed duration
- Subjects **positive** for active TB per workup are not eligible for the study
- Subjects **negative** for TB (no signs of latent or active TB) per workup may be enrolled in the study
- If the test result is **indeterminate**, it is **recommended to repeat the test once**. If a TB workup was conducted prior to the screening the subject, results of the workup can be used to assess eligibility if the workup was conducted within 12 weeks prior to enrollment.
  - If the second test is **negative**, the subject may be enrolled
  - If the second test is **positive or indeterminate**, the investigator should perform workup as per local guidelines.
    - Subjects **positive** for latent TB per workup may enter the study if sufficient treatment has been initiated according to local routine clinical practice and will be maintained for the prescribed duration
    - Subjects **positive** for active TB per workup are not eligible for the study
    - Subjects **negative** for TB (no signs of latent or active TB) per workup may be enrolled in the study

According to the current CDC and United States Preventative Task Force (USPTF), HIV testing is a routine “opt-out” test. (37) Routine two-step HIV testing will be performed according to Mayo Medical Laboratories protocol. The testing involves antibody screening of HIV-1/-2. (38) If non-reactive in a low-risk group no further testing is needed. If reactive, a confirmatory test is performed with Western blot analysis. In indeterminate cases, repeat testing is performed as well as immunofluorescence and antibody confirmation testing. If a subject tests positive to HIV they will not be enrolled in the study and will be referred for management of their HIV.

- If the HIV-1/-2 antibody test result is **negative** and the patient is not suspected to have an acute HIV infection, the subject may be enrolled in the study
- If the HIV -1/-2 test result is **positive**, the investigator should perform workup for the confirmation of the result as per guidelines
  - Subjects **positive** for HIV per workup are not eligible for the study
  - Subjects **negative** for HIV per workup may be enrolled in the study
- If the test result is **indeterminate or unreadable, further analysis is recommended**.
  - Secondary testing may be performed with repeated testing in 3 months, immunofluorescence, HIV quantitation
  - If the second test is **negative**, the subject may be enrolled
  - If the second test is **positive or indeterminate**, the investigator should perform workup as per guidelines.
    - Subjects **positive** for HIV are not eligible
    - Subjects **negative** for HIV per workup may be enrolled in the study

Hepatitis B screening will be performed on all patients. Initial screening will be performed following the Mayo Medical Laboratory Protocol with Hepatitis B surface antigen (HBsAg), Hepatitis B surface antibody (HBsAb), Hepatitis B Core antibody (HBcAb) as screening tests with reflex testing with Hepatitis B DNA detection and quantitation by PCR.

Hepatitis C screening will be performed on all patients. Initial screening will be performed following Mayo Medical Laboratory Protocol with Hepatitis C antibody screening with reflex Hepatitis C RNA detection and quantitation by PCR.

Coccidioidomycosis (cocci) is a fungus that is endemic to the southwest United States, with Phoenix and Tucson having some of the highest rates of cocci in the entire world. (39) It is our standard of practice to test for

cocci prior to prescribing any immunosuppressive medications. Cocci disseminates in less than 0.5% of individuals. However, dissemination in the immune-compromised population can occur in up to half of cases. (40) Therefore, individuals with untreated cocci will be excluded from this study.

We utilize a two-step testing process that involves an enzyme immunoassay (EIA), which tests for Immunoglobulin G (IgG) and IgM for an acute cocci infection as well as a chest x-ray (CXR) to assess for pulmonary infiltrates. (41) If the EIA is positive, a second confirmatory test with a complement fixation assay will be performed. If the test is negative, but there is a high index of suspicion (i.e. a distinct rash, cough symptoms, or an abnormal CXR) repeat cocci testing should be performed in 2-3 weeks. All of these laboratory studies are done routinely at Mayo Clinic Arizona Laboratory.

- If the EIA test result is **negative**, the CXR is normal, and there are no constitutional symptoms, the subject may be enrolled in the study
- If the test result is **positive**, the investigator should perform workup for the test result as per local procedures
  - Subjects **positive** for active cocci per workup are not eligible for the study
  - Subjects **negative** for cocci per workup may be enrolled in the study
- If the test result is **indeterminate** (i.e. constitutional symptoms with a negative EIA), it is recommended to **repeat the test once in 2-3 weeks**.
  - If the second test is **negative**, the subject may be enrolled
  - If the second test is **positive or indeterminate**, the investigator should perform workup as per local guidelines.
    - Subjects **positive** for cocci are not eligible
    - Subjects **negative** for cocci per workup may be enrolled in the study

A standard 12-lead ECG will be performed at screening. The investigator/qualified site staff must review and initial the tracing. The tracing must then be stored with the subject's source documents. If the ECG findings are clinically relevant and would prevent the subject from participating in the study (taking into account the subject's overall status as well as the medication profile), the subject should be recorded a screen failure and should not receive treatment.

A serum  $\beta$ -hCG test will be performed in all pre-menopausal women as indicated. All pre-menopausal women who are not sterile at screening will also have a serum pregnancy test performed locally as indicated. Any woman with a confirmed positive pregnancy test during screening is not eligible for the study. A positive urine pregnancy test during the treatment periods of the study requires immediate interruption of study treatment until serum  $\beta$ -hCG is performed and found to be negative. If the serum  $\beta$ -hCG test is positive, study treatment must be definitively discontinued.

### **Blood Pressure and Pulse:**

After the subject has been sitting for five minutes, with back supported and both feet placed on the floor, systolic and diastolic **blood pressure will be measured twice** (measurements separated by 1 to 2 minutes) using a validated device with an appropriately sized cuff and each BP measurement will be recorded. (42) In case the cuff sizes available are not large enough for the subject's arm circumference, a sphygmomanometer with an appropriately sized cuff may be used. The average of the two measurements will be recorded. If possible, the same study site staff member throughout the study should perform assessments.

Normal blood pressure will be defined as a systolic pressure of 90 to <120 mmHg, and a diastolic blood pressure of 60 to <80 mmHg under the measurement conditions outlined above. Notable blood pressure will be hypertension (systolic blood pressure of  $\geq 140$  mmHg and/or diastolic blood pressure of  $\geq 90$  mmHg) or hypotension (systolic blood pressure of <90 mmHg and/or a diastolic blood pressure of <60 mmHg). A blood pressure indicative of prehypertension (systolic blood pressure of 120 to <140 mmHg and/or diastolic blood pressure of 80 to <90 mmHg) will not be regarded as notable. (43)

A normal pulse rate will be defined as a rate of 60 to 100 beats per minute (bpm) under the measurement conditions outlined above. Notable pulse rates are a rate below 60 bpm (bradycardia) or above 100 bpm (tachycardia).

**Height and Weight:**

Height and body weight will be measured in indoor clothing, but without shoes. If possible, body weight assessments should be performed by the same study site staff member and using the same scale throughout the study.

**Blood Draws:**

Subjects should avoid smoking within the hour preceding the blood draws. All laboratory studies will be conducted within the Mayo Clinic Health Systems (Mayo Clinic Arizona and Mayo Clinic Rochester). Details on the collections, shipment of samples and reporting of results will follow Mayo Clinic's current protocols. For the identification of notable values, the Mayo Clinic reference laboratory should be consulted.

**Supplemental 3: Safety Monitoring**

**Infection monitoring:**

Study subjects will be evaluated at each visit for signs or symptoms of infection.

- Vitals signs as well as constitutional symptoms will be assessed.
- Assessment for common infections such as cellulitis as well as oral, vaginal, and cutaneous candidiasis will be performed

**Steroid monitoring:**

Study subject given prednisone will be assessed at each visit for signs of infection as well as elevated blood glucose.

- Unless contraindicated, all study subjects on prednisone will be placed on calcium 1200mg and vitamin D 800 IU daily.
- An endocrinologist will monitor those individuals with a history of diabetes.

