### **Research Design:**

This is a single center, exploratory, open-label, single-arm design study of 12 patients with BP. Treatment naïve and treatment refractory patients with BP will be treated with Taltz (Ixekizumab). Patients who are non-responders, to physician choice standard of care, will undergo a washout period and will be enrolled in the study. The washout period is 2 weeks for systemic non-immunosuppressive agents, topical steroids, and topical calcineurin inhibitors. A 4-week washout period will be used for systemic systemic immunosuppressive agents or 5 half-lives, whichever is longer, and no live vaccines should be administered within 12 weeks of the study drug. ([Table-1](#)) The study consists of 3 epochs: screening/washout period (of at least 1 week and up to 4 weeks), treatment epoch (of 12 weeks from screen/washout), and follow up epoch (of 6 weeks). The screening and washout period will allow for treatment naïve/ new diagnosis BP to undergo evaluation and diagnosis and for treatment refractory to undergo a washout. The total duration of the study will be 18 weeks.

The duration of treatment, 12 weeks, is based upon the maximal efficacy and dosing regimen of Taltz (Ixekizumab) in psoriasis.(7) Although psoriasis and BP are different disease processes, we would expect a response by 12 weeks of treatment. The open-label, single-arm design will allow for the assessment of the effects of Taltz (Ixekizumab) monotherapy in patients with acute and chronic disease in a relatively short time frame and will minimize study costs. This is critical as there may be a significant benefit either earlier or later in the disease course. This design will also allow for more patients to undergo targeted, serological analysis, which will provide in-vivo evidence of the pathogenesis of disease as well as the changes that occur during treatment. The open-label design of this study will have assessment bias on the part of the patient as well as the physician. The single-arm design will not allow for blinded assessment. In order to mitigate these issues, we will be using objective and validated methods of clinical assessment, which should be robust including: new blister formation, BPDAI, and prednisone usage. Additionally, the serological markers, which are secondary endpoints, will be assessed as an unbiased corollary to the primary effects of Taltz (Ixekizumab) on BP patients.

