### **Concomitant Medications:**

Concomitant medications are allowed if not listed in [Table-1](#). Oral corticosteroids will be allowed as a rescue medication. Stable doses of oral corticosteroids will be permitted at enrollment of the study, with a maximum dose not to exceed 20mg/day of prednisone or its equivalent. For patients on oral corticosteroids, Calcium 1200mg and Vitamin D 800 IU will be prescribed. For individuals with recurrent cellulitis or recurrent candidiasis, antimicrobials will be prescribed (see Exclusion Criteria). Dose adjustments of these medications should be avoided during the study. Drug-induced cases of BP will be excluded. Subjects who are receiving treatments known to worsen BP (angiotensin converting enzyme inhibitors & furosemide) must be on stable dose for at least 4 weeks prior to enrollment. Topical corticosteroids (TCS) are not allowed during the entirety of the study. Oral corticosteroids, as a rescue means (see [Supplemental 4](#)), will be allowed. After the screening period, the use of concomitant medication for BP in all body regions is restricted to bland emollients and other non-medicated interventions (not listed in [Table-1](#)) Use of bland emollients must be recorded. Preferred

emollients include Vaseline, Vanicream, and Vaniply. The definition of “bland” excludes all topical medications that contain pharmacologically active ingredients. Once the subject is screened and if the subject has intolerable blistering, scaling, and/or itching, the use of bland emollients is permitted. The use of bland emollients should be avoided during the 12 hours preceding a scheduled study visit.

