### **Safety Measures:**

A thorough baseline screening will be followed for all patients and is outlined in [Table-2](#). A detailed list of the methods in which baseline screening will be performed is outlined in [Supplemental 2](#). All blood draws and safety assessments must be performed **prior** to study treatment administration. Appropriate safety assessments (e.g., evaluation of AEs and SAEs) should be repeated after dosing with study treatment. A physical examination, including general appearance and vital signs, will be performed as indicated in [Table-2](#). If indicated, based on medical history and/or symptoms, additional exams will be performed at the discretion of the investigator. If possible, the same member of the study site staff throughout the study will perform assessments for an individual subject. Information for all physical examinations will be included in the source documentation at the study site. Significant findings that are present prior to the subject signing informed consent will be included in the Medical History. Significant findings made after the signing of the informed consent, which meet the definition of an AE, must be recorded as an AE. Vital signs (blood pressure, pulse, height, weight) will be assessed at each physical examination as indicated in [Table-2](#) (see [Supplemental 2](#) for details on how to acquire vital signs). Whether action needs to be taken to address notable vital signs will be decided by the investigator, taking into account the overall status of the subject. Laboratory studies will be drawn as indicated in [Table-2](#). Whether action needs to be taken to address notable laboratory values will be decided by the investigator, taking into account the overall status of the subject. Hematology assessments will be measured at all scheduled study visits specified in [Table-2](#). Serum chemistry will be a comprehensive metabolic panel will be measured at all scheduled study visits specified in [Table-2](#).

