#### **Supplemental 4: Corticosteroid Rescue**

Subjects will be evaluated at baseline and at 2 week follow ups for disease activity and severity. Those individuals scoring greater than 20 on the BPDAI pruritus component- VAS will be offered oral corticosteroids as follows:

- Corticosteroid Taper
  - Baseline
    - If BPDAI pruritus component- VAS greater than 20
      - Offer oral prednisone 20mg daily
      - If patient declines prednisone for any reason other than disease control this should be documented in the eCRF
  - At 2 week follow ups
    - If BPDAI pruritus component- VAS greater than 20
      - If prednisone naive
        - Offer to continue prednisone at 20mg daily
        - If patient declines prednisone for any reason other than disease control this should be documented in the eCRF
      - If currently on prednisone 20mg daily
        - Maintain on 20mg prednisone daily
        - If patient declines or decides to stop prednisone for any reason other than disease control this should be documented in the eCRF
      - If currently on 20mg prednisone every other day
        - Offer to increase prednisone at 20mg daily
        - If patient declines or decides to stop prednisone for any reason other than disease control this should be documented in the eCRF
    - If BPDAI pruritus component- VAS less than 20
      - If at 20mg daily
        - Taper prednisone to 20mg every other day

- If patient declines or decides to stop prednisone for any reason other than disease control this should be documented in the eCRF
  - If at tapered dose of 20mg every other day
    - Stop prednisone
    - If patient declines or decides to stop prednisone for any reason other than disease control this should be documented in the eCRF
- Calcium 1200mg and Vitamin D 800 IU will be prescribed along with oral corticosteroids and will be continued for the duration of the study once initiated

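### Subjects on prednisone are to be checked for raised glucose at each visit, but Table-2 schedules a test that could show it at only one of eight visits, and no chemistry after Week 8

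*Combined protocol and SAP*

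**What the plan says.** Supplemental 3, under Steroid monitoring, sets the duty: "Study subject given prednisone will be assessed at each visit for signs of infection as well as elevated blood glucose". It gives no test, specimen or threshold. It adds endocrinology monitoring, but only for subjects with a history of diabetes.

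The Safety Measures section describes chemistry testing: "Serum chemistry will be a comprehensive metabolic panel will be measured at all scheduled study visits specified in" Table-2. The body text therefore adds no visits of its own. In the table headed "Table-2: Screening and Visits", the CMP is marked at Screening and Week 8, and HbA1c at Screening. Blood is drawn at Screening, Day 0 and Weeks 4, 8 and 12. No row is labelled glucose or fingerstick.

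Prednisone can be in use at any point. Under Concomitant Medications, "Stable doses of oral corticosteroids will be permitted at enrollment of the study, with a maximum dose not to exceed 20mg/day of prednisone". Supplemental 4 then provides for rescue: "Subjects will be evaluated at baseline and at 2 week follow ups for disease activity and severity". A pruritus score above 20 at any of these visits leads to an offer of 20 mg daily.

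The Secondary Outcome Measures include clinical safety, assessed partly by laboratory variables.

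**The concern.** The protocol asks for a check at every visit on prednisone, and the schedule that staff will work from provides a suitable test at almost none of them. Without a named method, the check may be skipped, or reduced to asking about symptoms.

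The population makes this worth a line of text. The Introduction describes an elderly group in whom infection is a leading complication of treatment, and the exclusion criteria treat poorly controlled diabetes as a condition predisposing to infection. Supplemental 3 (Abnormal Labs) counts a laboratory abnormality as an adverse event only if it meets set criteria, and a value that is never measured cannot be judged against them.

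There is a related gap for all subjects. Chemistry contributes to the laboratory safety outcome at a single on-treatment visit, Week 8, with nothing at the end of treatment.

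**Working it through.** The plan states no figure to reproduce here; the check is a count of marks in Table-2.

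**Inputs**
- Visits from Day 0: Day 0, Weeks 2, 4, 6, 8, 10, 12 and 18 = 8.
- CMP: Screening, Week 8.
- HbA1c: Screening.
- Venipuncture from Day 0: Day 0, Weeks 4, 8, 12 = 4 visits.
- Ixekizumab: Day 0, Weeks 2, 4, 6, 8, 10, 12 = 7 dosing visits.
- Planned subjects: 12 (Sample Size Computation and Power Analysis).
- Assumption: the CMP includes glucose. The documents do not list its contents.

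The physical examination row fills all nine columns and the other rows line up with it, so the second CMP mark belongs to Week 8 and is not a shifted cell.

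**Present schedule**
- Visits from Day 0 with a glucose-bearing test: 1 of 8 (Week 8). If the CMP did not include glucose, it would be 0 of 8.
- Visits with no blood draw at all: 8 − 4 = 4 (Weeks 2, 6, 10, 18).
- A subject starting rescue at Day 0 passes Weeks 2, 4 and 6 without a scheduled glucose; the first comes at Week 8.
- A subject starting at Week 8 or later has no scheduled glucose at any later visit.
- Blood is drawn before dosing (Safety Measures), so the Week 8 panel follows 4 of the 7 dosing visits. The other 7 − 4 = 3 (Weeks 8, 10, 12) have no chemistry after them.

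**With the change**
- CMP at Weeks 4, 8 and 12: 3 of 8 visits, all on existing draws.
- Point-of-care glucose at the remaining visits for subjects then on prednisone: 8 − 3 = 5 (Day 0, Weeks 2, 6, 10, 18). Together, 3 + 5 = 8 of 8.
- The Week 12 panel, drawn before that day's dose, follows 6 of the 7 dosing visits.
- Extra panels: 2 × 12 = 24 at most.
- Fingersticks: 5 × 12 = 60 at most, if every subject were on prednisone at all five visits.

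**The case against.** The best reply is that the Steroid monitoring text is itself the instruction. A duty that applies only to subjects on prednisone need not appear in a schedule meant for everyone. Table-2 is not exhaustive: it has no row for vital signs or blister-fluid sampling, and the MRSA swab and candida culture sit in the exclusion criteria instead. On this view, 1 of 8 counts routine panels and does not measure how often the requirement will be met. This stands, and a reader who infers that the protocol contradicts itself, or that subjects will go unchecked, goes further than the documents do. What remains is that those other conditional tests are named in the text and the glucose test is not.

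Safeguards also exist: CMP and HbA1c at screening, a 20 mg daily rescue dose with a taper, endocrinology input for subjects with known diabetes, a physical examination at every visit, and further examinations at the investigator's discretion. With one center and 12 subjects, practice is unlikely to vary widely. These points lower the risk, but none supplies a glucose value at each visit in a subject without known diabetes. The discretionary examinations depend on history or symptoms, and the eligibility criteria set no HbA1c limit.

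It can also be said that a single sentence naming point-of-care glucose would meet the requirement with no change to Table-2. That is correct for the steroid check alone. The added panels are justified because they also supply later chemistry for the safety outcome, on blood already taken.

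**Conclusion.** The point holds as a minor, inexpensive safety improvement. From Day 0 to Week 18, 1 of 8 visits has a scheduled test that could show raised glucose, and chemistry stops at Week 8 while dosing continues to Week 12. The count rests on the CMP including glucose.

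Two further inferences are tempting and should be resisted. One is to turn the count into a share of visits on prednisone that would lack a glucose value. The documents do not say how many subjects will take prednisone or for how long, and subjects may decline it, stop early, restart or enter already on it. The other is to state a fixed interval between the screening glucose and Week 8. The plan gives only the length of the "screening/washout period (of at least 1 week and up to 4 weeks"), not the day within it on which the panel is drawn.

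The primary endpoint and the efficacy analyses do not use glucose and are not affected.

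**What to change.** 1. In Table-2, mark the CMP at Weeks 4 and 12.
2. In Supplemental 3 (Steroid monitoring), add one sentence: subjects on prednisone have a point-of-care glucose at each visit without a CMP.

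The cost is two marks and one sentence, at most 24 extra panels with no extra venipuncture, and a fingerstick only for subjects on prednisone at the visit concerned.
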